1.2. Other Efficacy Endpoints

The other efficacy endpoints are as follows:

- Change from baseline in the weekly average of total daily (24-hour) use of albuterol/salbutamol inhalation aerosol (number of inhalations) at weeks 4, 8, and 12
- Change from baseline in the percentage of rescue-free days (defined as 24-hour periods with no rescue medication usage) during the 12-week treatment period

- Change from baseline in the percentage of symptom-free days (defined as 24-hour periods with asthma symptom score of 0) during the 12-week treatment period
- Change from baseline in the percentage of asthma-control days (defined as 24-hour periods with asthma symptom score of 0 and no rescue medication usage) during the 12-week treatment period
- Change from baseline in 1-hour postdose percent predicted morning FEV₁ at week 1
- Change from baseline in the weekly average of daily evening PEF over the 12-week treatment period
- Change from baseline in the weekly average of the percent predicted trough morning FEV₁ at weeks 1, 2, 4 and 8
- Proportion of patients who achieve at least a 15% increase in morning FEV₁ at 1 hour postdose at day 1 (randomization visit [RV]/treatment visit [TV] 1), week 1, and week 12
- Change from baseline in asthma control (measured by C-ACT) score at weeks 4, 8, and 12
- Time to consistent onset of effect defined as the decrease from baseline in daily rescue medication use on 3 consecutive days

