2.4. Sample Size and Power Considerations

Sample size and power calculations are driven by demonstrating superiority of FS MDPI 50/12.5 mcg twice daily over Fp MDPI 50 mcg twice daily in change from baseline in 1-hour postdose percent predicted morning FEV₁ at week 12 and the superiority of Fp MDPI 50 mcg twice daily over placebo in change from baseline in percent predicted trough morning FEV₁ at week 12.

For the superiority comparison of FS MDPI 50/12.5 mcg twice daily versus Fp MDPI 50 mcg twice daily, assuming that the change from baseline in 1-hour postdose percent predicted morning FEV₁ at week 12 is analyzed using an ANOVA model with only a single factor of treatment group, the following assumptions were made:

- The initial assumed common standard deviation (SD) was 9.3% and the true treatment difference was 4.5% between FS MDPI 50/12.5 mcg twice daily and Fp MDPI 50 mcg twice daily. This assumption was based on data collected in previous Teva studies with the same Fp MDPI and FS MDPI products in adult asthma patients who completed the 12-week treatment period and based on office-based spirometry.
- The initial power was 97% at a 2-sided significance level of 5%.

For the superiority comparison of Fp MDPI 50 mcg twice daily versus placebo, assuming that the change from baseline in percent predicted trough morning FEV₁ at week 12 is analyzed using an analysis of variance (ANOVA) model with only a single factor of treatment group, the following assumptions were made:

- The initial assumed common standard deviation (SD) was 13.25% and the true treatment difference was 5% between Fp MDPI 50 mcg twice daily and placebo. This assumption was based on data collected in previous Teva studies with the same Fp MDPI product in adult asthma patients and based on office-based spirometry
- The initial power was 85% at a 2-sided significance level of 5%.

Study FSS-AS-30003 is the very first study in which a handheld spirometry device is utilized 1) as the primary endpoint in a Phase 3 study and 2) in a pediatric asthma patient population for a pivotal study of this scale. This made it difficult to predict the actual variability of the data. A blinded sample size reassessment was not planned. Routine blinded data monitoring of this study FSS-AS-30003 revealed that the SD for the overall study population is indeed higher than the initial assumptions. In addition, FEV₁ stability has been monitored closely throughout this study

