(see Clinical Study Protocol FSS-AS-30003 Section 6.1.3 for detail). A number of alerts were determined by the investigators as not related to worsening asthma but rather due to poor patients' effort, which has been challenging in this patient population as young as 4 years of age, despite the rigorous training and coaching provided by the investigators. To ensure the high quality of the FEV₁ data and integrity of the study, an unplanned blinded data quality evaluation and sample size reassessment was conducted. Some of the initial assumptions and the sample size described above were revised to the following:

- For the superiority comparison of FS MDPI 50/12.5 mcg twice daily versus Fp MDPI 50 mcg twice daily, the SD was revised to 22% and the overall mean change from baseline was revised to 6.5% (blinded SD observed after 427 patients completed week 12 of this study (excluding IMPD)) and the power down to 80%.
- With these assumptions, 181 patients per treatment group are required for the 2-sided test of FS MDPI 50/12.5 mcg twice daily and Fp MDPI 50 mcg twice daily.
- For the superiority comparison of Fp MDPI 50 mcg twice daily versus placebo, the SD was revised to 17% and overall mean change from baseline was 5% (blinded SD observed after 434 patients completed week 12 of this study (excluding IMPD) and the power was revised to 80%.
- With these assumptions, 181 patients per treatment group are required for the 2-sided test of Fp MDPI 50 mcg twice daily versus placebo.

Based on current blinded data and assuming a dropout rate of 12%, a total of 824 patients (206 patients per treatment group) will be randomized (initial assumption for dropout rate was 15%).

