6. EFFICACY ANALYSIS

6.1. General

The ITT analysis set will serve as the primary analysis set for all efficacy analyses, the PP population will serve as a supportive population for the primary efficacy analyses, as detailed below. Summaries will be presented by treatment group, unless specified otherwise.

Descriptive statistics (n, mean, SD, SE, median, min, and max) for efficacy variables and change from baseline will be provided by visit or week window, as appropriate. Final assessments will compare between treatment groups.

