The change from baseline in the percentage of asthma-control days (defined as 24-hour periods with asthma symptom scores of zero and no rescue medication use) during the 12-week treatment period will be summarized and compared between treatment groups using the Wilcoxon-Mann-Whitney test.

6.4.2.5. Change from Baseline in 1-Hour Postdose Percent Predicted Morning FEV₁ at Week 1

On the morning of the week 1 visit (TV2), patients will perform their predose FEV₁ assessment at the investigational center. They will take their morning dose of the IMP, and subsequently perform the 1-hour postdose FEV₁ measurements using the handheld device. Patients, who have been withdrawn from IMP but remain in the study, will be asked to perform the 1-hour postdose lung function assessments at the visit although patients will not be taking a dose of IMP. The assessment should be performed approximately 1 hour after the predose lung function assessments were obtained.

The change from baseline in 1-hour postdose percent predicted morning FEV₁ at week 1 will be analyzed using an ANCOVA model with effects due to baseline percent predicted FEV₁, sex, age, (pooled) investigational center, previous therapy (ICS or NCS), and treatment. In cases where the 1-hour postdose value is missing at week 1, the 1-hour postdose at baseline (RV/TV1) will be used.

6.4.2.6. Change from Baseline in the Weekly Average of the Daily Evening PEF Over the 12-week Treatment Period

The analysis of change from baseline in weekly average of daily evening PEF over the 12-week treatment period will be performed using an MMRM with effects due to baseline weekly average of daily evening PEF, sex, age, (pooled) investigational center, previous therapy (ICS or NCS), week, treatment, and week-by-treatment interaction. No explicit structure will be assumed for the covariance among the repeated measures. However, if there is a convergence problem with unstructured covariance, a compound symmetry covariance structure will be assumed.

6.4.2.7. Change from Baseline in Weekly Average of the Percent Predicted Trough Morning FEV₁ at weeks 1, 2, 4 and 8

The change from baseline in weekly average of the percent predicted trough morning FEV₁ will be summarized descriptively by week and treatment.

6.4.2.8. Proportion of Patients who Achieve at Least a 15% increase in morning FEV₁ at 1-hour postdose at Day 1 (RV/TV1), Week 1, and Week 12

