The proportion of patients who achieve at least a 15% increase in morning FEV₁ at 1-hour postdose at day 1 will be analyzed using a logistic regression model with effects due to previous therapy (ICS or NCS) and treatment. The proportion of patients who achieve at least a 12% increase in FEV₁ at 1-hour postdose at week 12 will be analyzed similarly.

6.4.2.9. Change from Baseline in Asthma Control (measure by C-ACT) score at Weeks 4, 8, and 12

The change from baseline in C-ACT score at weeks 4, 8 and 12 will be summarized descriptively by visit and treatment.

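### Day-1 1-hour postdose FEV₁ is tested only as a 15% responder cut without a baseline term; adding the week-1 ANCOVA at day 1 would cheaply recover power if the change is roughly normal

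*SAP*

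**What the plan says.** The 1-hour postdose FEV₁ is measured in clinic at RV/TV1, after a same-visit predose value (Protocol Table 3; SAP 4.2).

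- **Day 1.** SAP 6.4.2.8 classifies each child by whether FEV₁ rose by at least 15%. That proportion in "morning FEV₁ at 1-hour postdose at day 1 will be analyzed using a logistic regression model with effects due to previous therapy" and treatment. Baseline FEV₁ is not in the model.
- **Week 1.** SAP 1.2 lists a continuous endpoint, "Change from baseline in 1-hour postdose percent predicted morning FEV₁ at week 1". SAP 6.4.2.5 says it "will be analyzed using an ANCOVA model with effects due to baseline percent predicted FEV₁, sex, age, (pooled) investigational center, previous therapy" and treatment.
- **Week 12.** The continuous change is the endpoint of the first primary comparison, FS 50/12.5 versus Fp 50, again by ANCOVA with baseline (SAP 6.2.2.2 and Table 7).
- **Other day-1 output.** SAP 6.1 promises descriptive statistics only: they "for efficacy variables and change from baseline will be provided by visit or week window, as appropriate".

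SAP 7.2 makes no multiplicity adjustment for other efficacy analyses. Protocol 9.5.4.4 leaves the methods for these endpoints to the SAP.

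**The concern.** A cut at 15% keeps only which side of the line a child fell on and discards how far the child moved. With a roughly symmetric, light-tailed change this costs precision. Leaving out baseline FEV₁ can cost more, because the line sits at 15% of the child's own predose value: a child with a lower baseline needs a smaller absolute gain to count as a responder.

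The SAP gives no reason for treating day 1 differently from weeks 1 and 12. It even uses the day-1 1-hour value on the continuous scale when a week-1 value is missing (SAP 6.4.2.5).

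At stake is one piece of supportive evidence for the lead FS versus Fp 50 comparison. It is taken after the first dose, before IMP discontinuation and reference-based imputation come into play.

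**Working it through.** **1. Reproduce the plan's own figures (SAP 2.4).** The initial inputs were: "The initial assumed common standard deviation (SD) was 9.3% and the true treatment difference was 4.5"%. With 127 per arm (Protocol 16.1) I get 97.1% power, which matches "The initial power was 97% at a 2-sided significance level of 5"%. At the reassessment "the SD was revised to 22% and the overall mean change from baseline was revised to 6.5"%. The document calls 6.5 an overall mean change, but it acts as the treatment difference in the sample size: n = 2 × [(1.960 + 0.842) × 22 / 6.5]² ≈ 180, or 181 by the t-test; 181 / 0.88 ≈ 206. The stated 181 and 206 therefore reproduce. The documents state no power for the day-1 analysis.

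**2. Inputs for day 1.**
- n = 206 per arm, assuming every randomized child has a day-1 value.
- Difference d = 4.5 or 6.5, and SD 9.3 or 22, from the week-12 1-hour planning figures. Pairing 4.5 with 22 is my assumption; the documents do not make it.
- SD 13.25 and 17 come from the other primary endpoint (weekly home trough FEV₁, Fp versus placebo). They serve only as intermediate values.
- Mean change over the two arms 6.5 (3 as a variant).
- Baseline 60 to 80% predicted, inside the 40 to 85% randomization window for home values (Protocol 5.9). A 15% relative rise is then 9 to 12 points of percent predicted.

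**3. Formulas (normal change, two-sided 5%).**
- Full scale, no baseline gain: power = Φ(d / (SD√(2/n)) − 1.96).
- Responder rate = 1 − Φ((0.15 × baseline − arm mean) / SD), with arm means = mean change ± d/2. These rates go into the pooled-variance two-proportion power formula.

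**4. Worked case: d = 4.5, SD = 22, baseline 70.**
- Full scale: 22√(2/206) = 2.168; 4.5 / 2.168 − 1.96 = 0.116; power 54.6%.
- Cut at 10.5, arm means 4.25 and 8.75: responder rates 38.8% and 46.8%; power 37.5%.

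**5. Range over baseline 60 to 80.**

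| d | SD | mean change | full scale | 15% cut | loss (points) |
|---|---|---|---|---|---|
| 4.5 | 22 | 6.5 | 54.6% | 37–38% | 16.8–17.4 |
| 4.5 | 17 | 6.5 | 76.6% | 55–57% | 19.9–21.2 |
| 4.5 | 13.25 | 6.5 | 93.1% | 76–78% | 15.3–17.5 |
| 6.5 | 22 | 6.5 | 85.0% | 66% | 18.7–19.5 |
| 4.5 | 9.3 | 6.5 | 99.8% | 96–97% | 2.7–4.3 |
| 4.5 | 9.3 | 3 | 99.8% | 90–95% | 4.8–9.6 |

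**6. Baseline adjustment.** At d = 6.5, SD 22, if baseline explains 10 to 25% of the variance (assumed), ANCOVA power is 88.5 to 93.4%. That widens the gap to the unadjusted responder model.

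**7. Heavy tails.** Simulated with d = 4.5, mean change 6.5, baseline 70 and total SD near 22; power is full scale versus cut.
- 5% outliers (core SD 15, outlier SD 72): about 56–57% versus 63%.
- 10% outliers (core SD 16, outlier SD 51): about 52–54% versus 55–56%.
- t on 4 df: about 54–55% versus 56–57%.
- t on 5 df: 54% versus 51–52%.
- The 5% case after dropping values at or above 200% predicted (SAP 4.1) and, as a further assumption, values at or below 15%: 71% versus 63%.

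**The case against.** **The normal model is doubtful here.** Protocol 9.1 says the sample-size reassessment was triggered by nonphysiologic changes, and SAP 2.4 reports poor effort in young children. Artefacts may have inflated the SD of 22, and a responder cut resists outliers. This stands: step 7 shows the loss can disappear. The SAP 4.1 exclusion works the other way, but only for values of 200% predicted or more.

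**The inputs are borrowed.** A change over about an hour, supervised and on one device, may vary less than a 12-week change. If its SD is near 9.3, little is lost. This also stands.

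**The responder endpoint is legitimate.** Protocol 9.5.3 lists it for day 1 and lists the continuous change at week 1, not day 1. Fifteen percent is the trial's own bronchodilator-response threshold for randomization (Protocol 5.9), calculated as a relative change (Protocol 6.1.2). The covariates match those of the secondary logistic model (SAP 6.3.2.6). Dropping or demoting the endpoint would be a preference, so it should stay.

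**The salmeterol effect is tested elsewhere.** Week 12 carries it on the full scale as the first primary test, and week 1 has its own ANCOVA. The by-visit means and SDs would let a reader form an unadjusted day-1 difference. That limits the consequence but does not supply a prespecified, baseline-adjusted estimate.

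A reader might infer that day 1 is the cleanest test of salmeterol. The documents never say so. FS 50/12.5 and Fp 50 carry the same Fp dose, so their contrast is balanced for steroid at every visit.

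**Conclusion.** The structural point holds. The sole inferential day-1 analysis of 1-hour FEV₁ is a 15% cut without baseline, while the same measure gets a baseline-adjusted ANCOVA at weeks 1 and 12.

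Its size is conditional. With a roughly normal change and 206 per arm, the cut costs about 15 to 21 points of power for FS versus Fp 50 at assumed SDs of 13.25 to 22. At SD 9.3 it costs about 3 to 4 points, or 5 to 10 if the mean change is only 3. Useful baseline adjustment would widen the gap; heavy tails would shrink or remove it.

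Two stronger readings are not supported. One is a flat loss of 15 to 20 points: no day-1 SD, effect or responder rate is given, so no single figure can be attached to the plan. The other is that the lead FS claim is weakened: it rests on the week-12 ANCOVA, which this does not touch. This is a cheap improvement to a supportive analysis, not a defect in the primary evidence.

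**What to change.** Before unblinding, add to SAP 6.4.2 an ANCOVA of the day-1 change from clinic predose in 1-hour postdose percent predicted FEV₁. Use the SAP 6.4.2.5 model (baseline, sex, age, pooled center, previous therapy, treatment) and name the FS 50/12.5 versus Fp 50 contrast. Apply the SAP 4.1 implausible-value rule and analyse observed day-1 values; the week-1 rule that borrows the day-1 postdose value has no counterpart here.

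Keep the 15% responder analysis as the protocol lists it, and add baseline percent predicted FEV₁ to its logistic model.

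While SAP 6.4.2.8 is open, reconcile two separate slips: its heading says 15% at week 12 but its text says 12%, and it states no method for the week-1 responder endpoint.

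The cost is some SAP wording and one more run of an existing model on data already scheduled for collection. No alpha is spent. The downside is one more supportive analysis outside multiplicity control, to be labelled as such.

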6.4.2.10. Time to Consistent Onset of Effect in Daily Rescue Medication Use

The time to consistent onset of effect is defined as the number of days elapsed from the date of randomization to the first date of 3 consecutive days with a decrease from baseline in daily rescue medication use. Patients who have 3 consecutive days with a decrease in effect will be counted as an event in the analysis, otherwise, patients will be right-censored at the date of last IMPDV assessments.

The analysis of time to consistent onset of effect will be performed using a log-rank test to compare the survival curves. Time to first onset of effect will be graphically displayed with a Kaplan-Meier figure and the median time to first onset and associated 95% CIs will be provided.

7. MULTIPLE COMPARISONS AND MULTIPLICITY

7.1. Multiple Comparisons for the Primary Analysis

For the analysis of the co-primary endpoints, a fixed-sequence multiple testing procedure will be employed to control the overall Type I error rate at the 0.05 level, as described in [Table 7](#). Specifically, treatment comparisons will begin with the first primary endpoint, [1] 1-hour postdose percent predicted morning FEV₁ at week 12 at the FS MDPI 50/12.5 versus Fp MDPI 50 mcg. If the resulting p-value is less than 0.05, then the next comparison of interest will be made, according to the direction of the arrow. This process will continue until the point where the p-value is greater than 0.05 at which no further comparisons will be interpreted inferentially.

Taking into consideration that this is the very first study that utilizes the handheld device in a large Phase 3 study in a pediatric asthma patient population (4 through 11 years of age), an unplanned blinded sample size re-assessment was conducted. Since the adjustment to sample size was based on blinded standard deviation, no adjustment to the multiplicity control is warranted.

No multiplicity adjustment will be made for sensitivity analyses of the primary endpoints or subgroups.

Table 7: Multiple Testing Procedures

Sequence	Primary Endpoint	Hypothesis Testing
1	[1] Change from baseline in 1-hour postdose percent predicted morning FEV ₁ at week 12	FS MDPI 50/12.5 mcg BID vs. Fp MDPI 50 mcg BID
		↓
2	[2] Change from baseline in weekly average of the percent predicted trough morning FEV ₁ at week 12	Fp MDPI 50 mcg BID vs. Placebo
		↓
3	[2] Change from baseline in weekly average of the percent predicted trough morning FEV ₁ at week 12	Fp MDPI 25 mcg BID vs. Placebo

FEV₁= forced expiratory volume in 1 second; FS MDPI = fluticasone propionate/salmeterol xinafoate multidose dry powder inhaler, Fp MDPI = fluticasone propionate multidose dry powder inhaler.

7.2. Multiple Comparisons for the Secondary Analysis

If the p-value is less than 0.05 for the 3 inferential comparisons in the primary analysis, inferential testing will be extended to the secondary analysis.

Testing of secondary efficacy variables for the study drugs will be performed in the sequential manner described in [Table 8](#) (Fp MDPI) and [Table 9](#) (FS MDPI).

Treatment comparisons will begin with the change from baseline in weekly average of daily trough morning PEF (first secondary endpoint) with Fp MDPI 50 mcg versus placebo for

Fp MDPI, or FS MDPI 50/12.5 mcg versus placebo for FS MDPI. If the resulting p-value is less than 0.05, the next comparison(s) of interest will be made according to the direction of the arrows. To the right, this will be the same endpoint to compare Fp MDPI 25 mcg versus placebo (Fp MDPI), or FS MDPI 50/12.5 mcg versus Fp MDPI 25 mcg (FS MDPI). To the next endpoint, this will be the change from baseline in the weekly average of the total daily (24-hour) use of albuterol/salbutamol inhalation aerosol (second secondary endpoint) at the Fp MDPI 50 mcg versus placebo (Fp MDPI), or FS MDPI 50/12.5 mcg versus placebo (FS MDPI).

This process will continue testing sequentially through the next study drug/strength for each variable and at a given strength through the order presented in [Table 8](#) and [Table 9](#) until either all comparisons of interest are made, or until the point at which the resulting p-value for a comparison is greater than 0.05. At the point where the p-value is greater than 0.05, no further comparisons of either that strength or that measure can be made. This procedure allows for control of the Type I error for comparisons at a particular study drug/strength over the 6 secondary endpoints, as well as comparisons over study drugs/strengths within a particular endpoint. However, it does not control the overall Type I error, nominal p-value will be reported.

No multiplicity adjustment will be made for other efficacy analyses.

Table 8: Sequence of Testing Secondary Endpoints for Fp MDPI

Secondary Endpoint	Hypothesis Testing	
	Fp MDPI 50 mcg vs. Placebo	Fp MDPI 25 mcg vs. Placebo
[A] Change from baseline in weekly average of daily trough morning PEF over the 12-week treatment period	↓ →	↓
[B] Change from baseline in the weekly average of total daily (24-hour) use of albuterol /salbutamol inhalation aerosol (number of inhalations) over weeks 1 through 12	↓ →	↓
[C] Change from baseline in the weekly average of the total daily asthma symptom score over weeks 1 through 12	↓ →	↓
[D] Change from baseline in asthma control (measured by C-ACT) score over the 12-week treatment period	↓ →	↓
[E] Time to first onset of effect defined as the first decrease from baseline in daily rescue medication use	↓ →	↓
[F] Proportion of patients discontinued from IMP for asthma exacerbation during the 12-week treatment period	→	

Table 9: Sequence of Testing Secondary Endpoints for FS MDPI

Secondary Endpoint	Hypothesis Testing		
	FS MDPI 50/12.5 mcg vs. Placebo	FS MDPI 50/12.5 mcg vs. Fp MDPI 25 mcg	FS MDPI 50/12.5 mcg vs. Fp MDPI 50 mcg
[A] Change from baseline in weekly average of daily trough morning PEF over the 12-week treatment period	↓ →	↓ →	↓
[B] Change from baseline in the weekly average of total daily (24-hour) use of albuterol /salbutamol inhalation aerosol (number of inhalations) over weeks 1 through 12	↓ →	↓ →	↓
[C] Change from baseline in the weekly average of the total daily asthma symptom score over weeks 1 through 12	↓ →	↓ →	↓
[D] Change from baseline in asthma control (measured by C-ACT) score over the 12-week treatment period	↓ →	↓ →	↓
[E] Time to first onset of effect defined as the first decrease from baseline in daily rescue medication use	↓ →	↓ →	↓
[F] Proportion of patients discontinued from IMP for asthma exacerbation during the 12-week treatment period	→	→	

